# 5.12 Safety Analyses

The safety analyses will be presented by the treatment received for the Safety Analysis Set.

#### 5.12.1 Summary

All safety analyses will be performed on the SAF.

Endpoint	Statistical Analysis Methods
AEs	AEs will be coded using the Medical Dictionary for Regulatory Activities (MedDRA) version 20.0 or later and summarized descriptively. Only TEAEs will be included in the main safety analysis. A TEAE is defined as any AE that has an onset on or after the first dose of study drug and before the last dose of study drug + 30 days or is any pre-existing AE that has worsened in severity on or after the first dose of study drug and before the last dose of study drug + 30 days. The incidence, nature, severity, relatedness, duration, outcome, seriousness and expectedness of TEAEs will be tabulated. AEs of special interest will be additionally separately tabulated.
Prior, concomitant and subsequent medications	Medications will be coded using WHO Drug dictionary and summarized descriptively using ATC level and preferred term. See Section 5.12.3 for further details.
Rescue medications	Rescue medications will be coded and summarized similarly to prior and concomitant medications. An additional summary of the use of rescue medication overlapping with each visit will be presented. See Section 5.12.4 for further details.
Need for additional glucocorticoid doses	Use of hydrocortisone from the stress dosing packs or use of any additional glucocorticoid treatment during the study will be summarized descriptively.
Other safety assessments	For laboratory parameters, vital signs, and ECGs, change from baseline will be calculated at each scheduled post-baseline visit and summary statistics will be presented both for absolute values (at baseline and each scheduled post- baseline visit) and changes from baseline by treatment arm, and visit. Shift tables of baseline to minimum and maximum on-treatment will be produced for the appropriate parameters displaying the number and percentage of participants in each of the categories (High, Low and Normal) relative to the category of their baseline assessment. Results considered clinically significant by the Investigator will be summarized at each visit. Physical examination results, and their change from baseline, will be summarized at each visit.

#### 5.12.2 Adverse Events

A treatment emergent adverse event (TEAE) is defined as:

- Any AE that has an onset on or after the first dose of study drug and before last dose of study drug + 30 days.
- Any pre-existing AE that has worsened in severity on or after the first dose of study drug and before the last dose of study drug + 30 days.

A TEAE which starts or worsens on or after the first dose of IRHC in the run-in period but before the first dose of randomized study treatment is allocated to the run-in period. A TEAE which starts or worsens after the first dose of randomized study treatment is allocated to the treatment actually received during the randomized treatment period. A TEAE which starts or worsens in the run-in period and worsens in the randomized treatment period is allocated to both periods.

A treatment-related AE is defined as an AE that is recorded by the Investigator as definitely, probably, possibly or likely to be related to the study drug. If an AE has missing relationship it is assumed to be related to the study drug for analysis purposes. Maximum severity will be assumed for an AE with missing severity.

TEAEs will be summarized separately for the run-in period and after randomization. In the list of AE tables below, only the first 2 will be done for both the run-in period and after randomization. All the others will just be done after randomization.

The following tables will be presented for AEs by treatment group:

- Overall incidence and the number of AEs, Serious Adverse Events (SAEs), Treatment related TEAEs, TEAEs leading to withdrawal of study drug, TEAEs leading to early withdrawal from study, TEAEs leading to study drug dose increase or decrease, TEAEs leading to study drug dose interruption, TEAEs leading to use of rescue medication, Treatment Emergent AEs of Special Interest (TEAESIs), non-treatment emergent AEs occurring > 30 days after last dose of study drug, and AEs leading to death run-in period and after randomization
- TEAEs by system organ class (SOC) and preferred term (PT), incidence and number of events run-in period and after randomization
- Treatment related TEAEs by SOC and PT, incidence and number of events after randomization only
- Serious TEAEs by SOC and PT, incidence and number of events after randomization only
- TEAEs by SOC, PT and maximum severity, incidence after randomization only

- Treatment related TEAEs by SOC, PT and maximum severity, incidence after randomization only
- TEAEs by SOC, PT and relationship, incidence after randomization only
- TEAEs leading to withdrawal of study drug by SOC and PT, incidence after randomization only
- TEAEs leading to study drug dose increase or decrease by SOC and PT, incidence after randomization only
- TEAEs leading to study drug dose interruption by SOC and PT, incidence after randomization only
- TEAEs leading to use of rescue medication by SOC and PT, incidence after randomization only
- TEAEs leading to early withdrawal from study by SOC and PT, incidence after randomization only
- TEAESIs (including events of unexpected benefit, adrenal crises, signs and symptoms of adrenal insufficiency and over-treatment) by SOC and PT, incidence after randomization only
- Non-treatment emergent AEs occurring > 30 days after last dose of study drug by SOC and PT, incidence after randomization only
- Listing of Serious TEAEs (presented in the Table section of the appendices)
- Listing of Deaths (presented in the Table section of the appendices).

In counting the number of AEs reported, a continuous event (i.e. reported more than once and which did not cease), will be counted only once; non-continuous AE reported several times by the same participant will be counted as multiple events.

For incidence summaries by SOC and PT, a participant will be counted only once at the SOC level and once at each PT level within the SOC level, even if the participant experienced more than one AE within a specific SOC and PT. For summaries by SOC, PT, and severity, a participant is typically counted once at each severity level for which the event occurred at the SOC level and at each severity level for which the event occurred for each unique PT within that SOC level. Therefore, participants may contribute to multiple severity levels within a PT or SOC.

All AEs will be listed.

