8.1.3. Visit 3 (Titration Visit - Week 4 + 1 Week)

Four weeks after the previous visit (+ 1 week), the participant will be requested to attend the study site for testing of androgen levels (if necessary this visit can be conducted as a domiciliary visit). Prior to the visit, the site staff should contact the participant to check that 'stress dosing rules' have not been applied in the 5 days preceding the visit date. If 'stress dosing rules' have been applied, then the visit should be postponed until the participant has been receiving no stress dosing medication for 5 days. The participant will be instructed to bring any empty packaging and any unused study medication and the emergency treatment pack with them to the visit for accountability purposes (note: participants take unused study medication and emergency treatment pack back home with them to use until the dose titration decision is made and new study medication dispensed). The participants will be told not to take their morning dose of study medication before attending for the visit (the morning dose will be taken after the 08:00 hour androgen sample and optional saliva sample [where applicable]). Male participants will be asked not to take multivitamins or dietary supplements containing biotin or vitamin B7 for 12 hours prior to the visit (to avoid interference with LH test results).

The following assessments will be carried out and recorded at this visit:

- Record the details of the participant's glucocorticoid doses for the previous 24 hours and throughout the visit
- Participants will be asked about any AEs (including events considered to be of unexpected benefit) and concomitant medications changes since the last visit
- Vital signs (BP, HR, respiratory rate and body temperature. BP to be recorded after the participant has been semi-supine for 10 minutes)
- Abbreviated physical examination (if indicated by AEs)
- Height, weight, and waist circumference will be measured
- Assessment of menstrual cycle changes in all pre-menopausal women
- Assessment of hirsutism by female participants using a VAS and by Investigators using Ferriman-Gallwey score (the Investigator can assess this via a video call if a domiciliary visit is conducted for this visit [within ±2 days of the domiciliary visit])

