8.4.8. Adverse Events of Special Interest

Some of the AEs likely to occur in participants with CAH are of special interest (adverse events of special interest [AESI]). These AESIs will be recorded in the eCRF and will also be reported to the Sponsor using the SAE/AESI form (see Appendix 3 for further details). These events will include, but not be limited to:

- any events causing implementation of 'stress dosing rules'
- Addisonian crisis, with Addisonian or adrenal crisis being defined as follows (based on Allolio, 2015):
 - (A): Major impairment of general health with at least 2 of the following signs/symptoms:
 - Hypotension (systolic blood pressure <100 mmHg)
 - Nausea or vomiting
 - Severe fatigue
 - Fever
 - Somnolence
 - Hyponatremia (<132 mmol/L) or hyperkalemia (as judged by characteristic ECG changes)

Hypoglycemia

AND

(B): Parenteral glucocorticoid (hydrocortisone) administration followed by clinical improvement including:

Outpatient care only

Hospital care (general ward)

Admission to intensive care unit

OR

Death from adrenal crisis (with or without parenteral glucocorticoid administration)

- any other event that is considered to be an unexpected benefit (note: events recorded as efficacy assessments e.g. change in menses, acne and hirsutism, should not be recorded as AESIs to avoid duplication)

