• To compare Chronocort to IRHC in terms of the impact on quality of life (QoL) using the self-completed Medical Outcome Study 36-Item Short Form Health Survey (SF- 36 ® ) total score and the sub-domain of vitality.	• The change from baseline to 4, 10, 16 and 28 weeks of randomized treatment in QoL using the self-completed SF-36® total score and the sub-domain of vitality will be summarized and compared between treatment arms.
• To compare Chronocort to IRHC in terms of the impact on QoL using the Multidimensional Assessment of Fatigue (MAF).	• The change from baseline to 4, 10, 16 and 28 weeks of randomized treatment in QoL using the MAF will be summarized and compared between treatment arms.

 
To compare Chronocort to IRHC in terms of the impact on QoL using the 5-level Standardized Health Questionnaire (EQ-5D-5LTM).
 
	• The change from baseline to 4, 10, 16 and 28 weeks of randomized treatment in QoL using the EQ-5D-5L ™ will be summarized and compared between treatment arms.
Compliance	
• To assess compliance over the study period.	• The percentage overall treatment compliance will be summarized.
Exploratory Efficacy	

Version 4.0: 22 Feb 2024

Safety	•
• To assess the safety and tolerability of Chronocort relative to IRHC.	• The incidence, nature, severity, relatedness, duration, outcome, seriousness and expectedness of treatment emergent adverse events (TEAEs) will be tabulated by treatment arm. AEs of special interest will additionally be tabulated separately, with particular note of adrenal crises.
• To assess the need for use of additional glucocorticoid doses (stress dosing rules).	• The use of medication from the stress dosing packs or use of any additional glucocorticoid treatment during the study will be tabulated by treatment arm.
• To evaluate the safety of Chronocort compared to IRHC by assessment of routine safety laboratory assessments, physical examination, vital signs, and electrocardiogram (ECG).	• Safety hematology, biochemistry, urinalysis, and vital signs conducted at each post-randomization visit and the physical examination and ECG assessments conducted after 28 weeks of randomized treatment, and their changes from baseline, will be summarized by treatment arm.

 This description aligns with the ICH E9 requirement for the definition of an Estimand. Outcome variables are underlined

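### The planned TEAESI line and table pool unexpected benefits with adrenal crises, so neither the line nor a mixed SOC total can be read as harm by arm

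*SAP*

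**What the plan says.** Protocol 8.4.8 defines a mixed class of adverse events of special interest (AESIs). It contains "any events causing implementation of" the stress dosing rules, adrenal crisis with a clinical case definition, and "any other event that is considered to be an unexpected benefit". On recording, it says: "These AESIs will be recorded in the eCRF and will also be reported to the Sponsor using the SAE/AESI form". One carve-out applies: "events recorded as efficacy assessments e.g. change in menses, acne and hirsutism, should not be recorded as AESIs to avoid duplication".

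Benefits come in through the adverse event question. Protocol 8.1.3 (Visit 3) says "Participants will be asked about any AEs (including events considered to be of unexpected benefit", and 8.1.5 and 8.1.7 (Visits 4 and 5) use the same wording. The corresponding item at Visit 6 (8.1.10) has no benefit prompt.

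SAP section 2 states the reporting aim: "AEs of special interest will additionally be tabulated separately, with particular note of adrenal crises". SAP 5.12.2 then lists the outputs. The overall summary gives the class a single entry in a run of items, "Treatment Emergent AEs of Special Interest (TEAESIs), non-treatment emergent AEs occurring" more than 30 days after the last dose. Further down there is one table: "TEAESIs (including events of unexpected benefit, adrenal crises, signs and symptoms of adrenal insufficiency and over-treatment) by SOC and PT". It gives incidence only, and only after randomization.

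The same SAP section treats an adverse event with missing relationship as related, and one with missing severity as being of maximum severity.

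**The concern.** An adverse event is by definition untoward (Protocol Appendix 3), yet the plan treats an unexpected benefit as a treatment-emergent adverse event of special interest. Once it is counted with adrenal crises, the total has no clinical direction: more can mean better or worse.

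The responder endpoints reward lower doses (Protocol 9.1.1 and 9.1.2), so harm from under-replacement is a natural counterweight, and a reader will look for it by arm in the AESI outputs. A mixed total is open to misreading there. The special note on adrenal crises also depends on this pooled table, which has no row built from the protocol's definition of a crisis.

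**Working it through.** The plan states no event figure here, so there is nothing to reproduce. The check compares passages and counts outputs.

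**1. Does a benefit become a treatment-emergent AE in the data?** Protocol 8.4.8 makes it an AESI recorded in the eCRF, the visit sections ask for it under AEs, and SAP 5.12.2 names it inside the treatment-emergent class. Nothing visible in SAP 5.12.1 or 5.12.2 takes it out again.

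**2. Which listed tables does it enter?** SAP 5.12.2 lists 14 tables and 2 listings. A post-randomization benefit record that is not serious and led to no action falls into:
- the overall summary
- TEAEs by SOC and PT
- TEAEs by maximum severity
- TEAEs by relationship
- TEAESIs by SOC and PT

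That is 5 of 14. If it is rated related, it also enters the treatment-related table and the treatment-related table by maximum severity: 5 + 2 = 7 of 14.

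**3. What do the missing-value rules do?** Appendix 3 grades intensity by discomfort and interference with activities, which does not fit a benefit. If severity or relationship is left blank, the SAP rules make the record maximum-severity or related. How often this would happen is unknown.

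**4. How are crises shown?** The protocol definition requires major impairment of general health with at least two listed signs, plus parenteral glucocorticoid followed by improvement; or death from the crisis. The TEAESI table is sorted by coded term, and no stated rule links terms to that definition. A preferred-term row therefore need not equal the number of events meeting it. Because the table gives incidence only, repeat crises in one participant count once there.

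**5. What can an unsplit line hide?** Counts here are assumed, since the documents give none. Let *c* be participants with a crisis and *b* participants with a benefit, one event each, no other AESIs, and *n* = 25 per arm (the planned arm size).
- Line difference = (c_A + b_A)/n − (c_B + b_B)/n
- Crisis difference = (c_A − c_B)/n

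With arm A at c = 4, b = 1 and arm B at c = 1, b = 4:
- Line: 5/25 − 5/25 = 20.0% − 20.0% = 0
- Crises: 4/25 − 1/25 = 16.0% − 4.0% = 12 points

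Holding each arm's total at 5, the crisis difference can lie anywhere from (0 − 5)/25 = −20 to (5 − 0)/25 = +20 points while the line shows 0. This shows that the line carries no information on the split. It does not forecast the data.

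**6. How large is the inflow of benefits?** They are prompted at 3 of the 4 post-randomization visits, and benefits already captured as efficacy assessments are excluded. What remains is a residual class in a trial of about 50 participants.

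**The case against.** The strongest reply is that harm can be read elsewhere. A non-fatal crisis needs parenteral glucocorticoid under Protocol 8.4.8, and SAP 5.12.4 lists injectable hydrocortisone as rescue medication. Such a crisis should therefore appear under TEAEs leading to rescue medication, which has its own line in the same overall summary and its own table. A benefit would not be expected in either. Fatal crises go to the deaths listing, and crises meeting SAE criteria go to the serious TEAE table and listing. Differently coded events have separate PT rows, all AEs are listed, and the TEAESI table's title discloses the benefits. Adrenal crises are named in a listed output, and SAP section 2 does not promise a dedicated table in so many words.

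Most of this stands. A reader might infer that the plan would conceal an imbalance in crises, or that it provides no crisis output at all; the documents support neither. In the example above, the adjacent rescue-medication line would be expected to separate the arms. What the reply does not repair is the pooled line, mixed SOC totals and the lack of a count by the protocol definition. The rescue-medication outputs cover any stress dosing, including for fever (Protocol Appendix 6), so they are not a count of crises either.

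It can also be said that benefits may not be stored as ordinary TEAEs, since an AE is untoward. The SAP's own label for the class points the other way, but table shells were not available to settle it.

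**Conclusion.** The point holds as a minor one. Followed as written, SAP 5.12.2 produces a TEAESI line, and possibly SOC totals and general TEAE counts, that mix benefit with harm. It also leaves adrenal crises without a row based on the protocol's definition. The measurable extent is 5 of 14 listed tables touched, or 7 if the record is rated related or defaults to related. These are counts of outputs, not of distortion. All are descriptive, and no test or efficacy conclusion changes.

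This rests on two assumptions: that benefit records sit in the AE data as the visit sections and 8.4.8 indicate, and that no unseen table shell already splits them.

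Two stronger readings are not supported:
- **A direction of bias.** Protocol 2.2 reports fewer crises and more therapeutic benefits in earlier studies, but without rates. Neither size nor direction of any between-arm effect in this trial can be derived.
- **A misleading adrenal-insufficiency row.** Protocol 8.4 does not require certain checklist symptoms to be reported as AEs, so a reader might infer that such a row would be incomplete. The planned table has SOC and PT rows, with no insufficiency category row to misread. A checklist summary in SAP text that is not visible cannot be ruled out, and SAP 5.3.1 lists all data in any case.

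**What to change.** In SAP 5.12.2:

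1. Tabulate unexpected-benefit records separately by arm, and exclude them from the TEAE, severity, relationship and harm-type AESI counts. If the AE data carry no benefit flag, classify the records blinded at the Data Review Meeting (SAP 5.5), using the SAE/AESI forms.
2. Split the TEAESI line and table by category. Give events meeting the Protocol 8.4.8 definition of adrenal crisis their own row, showing participants and number of events by arm.

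The cost is some SAP wording, a little extra programming and one blinded classification step before database lock. Data collection does not change. If lock has passed, SAP section 5 allows additional, justified tables in the CSR.

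As a note only: Protocol 8.4, which does not require some CAH-related checklist symptoms to be reported as AEs, and 8.4.7, which says there are no disease-related events outside AE reporting, should be reconciled. AE tables show adrenal-insufficiency symptoms only where they were reported as AEs.

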# 5.12.3 Prior, Concomitant and Subsequent Medication

Medications/procedures will be coded using the World Health Organization Drug Dictionary (WHODrug). The dictionary version used will be displayed in the footnote of the presented data displays.

# 5.12.3.1 Prior and Concomitant Medications

Separate tabulations will be produced for prior and concomitant medications presented by treatment group and overall, for the SAF.

Prior medications are defined as all medications with stop date after the signing of the informed consent form but before first dose of randomized study drug. Concomitant medications are defined as medications that either start after the first dose of randomized study drug, or started before the first dose of randomized study drug and continue to be taken after the first dose of randomized study drug. For details on imputation of missing/partial start and stop dates of prior/concomitant medications, see Section 5.2.7.

Participant incidence will be tabulated for concomitant medications by Anatomic Therapeutic Class (ATC) level 3 and preferred term for the SAF, by treatment group and overall. Participants will be counted only once for each ATC or preferred term in the event that they have multiple records of the same ATC or preferred term in the database. Prior medications will only be included in data listings.

Prior and concomitant medications will be listed with the occurrence (prior versus concomitant) identified.

Medications for CAH taken in the 26 weeks before the start of the run-in period will be separately listed and summarized.

# 5.12.3.2 Subsequent Medication

Medications that start after the last dose of randomized study drug but before 28 weeks after randomization are considered subsequent medications. Subsequent medications will be analyzed in the same way as concomitant medications (using ATC and preferred term, by treatment group and overall for the SAF), and will be included in the above listings of prior/concomitant/subsequent.

#### 5.12.4 Rescue Medication

Medication to be used when the 'stress dosing rules' are implemented will be supplied by the study site as part of an emergency treatment pack. The content will typically include (according to local practice):

- A one-week supply of 10 mg oral hydrocortisone tablets (to allow dosage of up to 60 mg daily)
- Hydrocortisone for injection plus syringes and needles
- The standard information guidance regarding 'stress dosing rules'.

Participants receiving rescue medication will be presented in a data listing. The extent of receipt of rescue medication in relation to efficacy assessments will be covered under Section 5.11.4.2. The Data Review will document further details of all medications regarded as rescue, and their timing.

Medications defined as rescue will be analyzed in the same way as concomitant medications (using ATC and preferred term, by treatment group and overall, for the SAF); however the number of separate uses (similar to presentation of the number of events for the AEs) will also be included. Rescue medications will be listed separately to prior, concomitant, and subsequent medications.

